### 6.8.1 Blinded and unblinded staff at trial sites

Trial procedures will be distributed between blinded and unblinded staff at participating sites detailed in the table below. All participating sites will have an unblinded PI and a blinded PI.

Unblinded procedures	Blinded procedures
Jeopardy Score (eligibility)	Baseline data part 1
Eligibility criteria (inclusion and exclusion)	Baseline data part 2
Participant registration form (eCRF only)	Medical History part 1
Informed Consent Form	Medical History part 2
Randomisation	Baseline ECG and Echo
Procedure visit part 1	Baseline bloods
Procedure visit part 2	Cardiac medication at baseline
PCI report	Baseline KCCQ
PCI details	Cardiac medication pre-procedure
PCI Summary	Pre-procedure KCCQ
Post-PCI coronary anatomy	Post procedure ECG and Troponin
Post-PCI Jeopardy Score	Discharge
	3 month follow up
	Cardiac medication at 3 months
	3-month KCCQ
	6 month follow up
	Cardiac medication at 6 months
	6-month KCCQ

### 6.8.2 Randomisation notification emails

Randomisation notifications containing treatment allocation will only be sent to unblinded staff at each site.

Randomisation notifications not containing treatment allocation will be sent to blinded staff at each site.

### **6.8.3 Blinding of the procedure**

Blinding will be achieved using the protocol developed and validated for placebo PCI procedures in the ORBITA and ORBITA-2 trials. Incremental doses of benzodiazepines and opiates will be administered for sedation with auditory isolation via headphones.

A generic discharge letter will be issued stating that the patient is enrolled in the REPRIEVED double-blind trial. A generic procedure report will be kept in the patient notes; after documenting details of the diagnostic angiogram and physiology, the report should state "The patient then underwent randomisation in the REPRIEVED trial. Details of the randomised allocation and any procedure performed were recorded in the trial eCRF. In case of a need for emergency unblinding, please contact [name]. For other queries please contact the local Principal Investigator, local research team or CTU at [contact]".

After the procedure, the participant will receive either clopidogrel or placebo clopidogrel, depending on treatment assignment. The unblinded PI and catheter lab team will have no further input into the care or follow up of the patient, outside of the procedures for emergency unblinding outlined below. A procedure report with the details of treatment completed will be documented in the eCRF only. At the end of the 6-month follow-up and after the participant has been unblinded, a copy of the procedure report will be stored in the patient notes.

CTU staff will be blinded to treatment assignment apart from agreed staff members such as the trial statistician and data manager. Criteria and procedures for emergency unblinding are outlined below and specified in the relevant working practice document (WPD). Unblinding will be managed via the Sealed Envelope eCRF system.

The efficacy of blinding for participants will be tested and reported using the blinding index at discharge from the randomisation procedure.

### **6.8.4 Emergency unblinding**

If a treating clinician believes they need to be unblinded to the patient's treatment arm they will contact the 24-hour unblinding telephone service to discuss the reasons for the unblinding request.

If, after discussing with the trial team, the patient's treating clinician's final decision is that the participant's safety will be compromised if they remain blinded to the treatment, then unblinding will take place. The authorised person to perform unblinding will use the eCRF system to request unblinding and will need to enter the reason for unblinding. The treating clinician will be notified of the participant's allocated treatment.

The unblinding will be recorded within the eCRF system, and an unblinding report will be produced from this for reporting unblinding to the Sponsor and the Data Monitoring Committee (DMC). All unblinding will be mentioned in the final trial report. Full unblinding procedures will be detailed in the relevant WPD.

## **6.9 Internal pilot study**

The trial will include a 12-month internal pilot phase to confirm the feasibility of REPRIEVED. Perceived major risks to recruitment are; whether the expected proportion of screened patients have significant coronary artery disease (CAD), whether participants will consent to enrolment and whether there is a risk of emergency unblinding;

	Red	Amber	Green
Number of participants recruited	<30	30-50	>50
Blinding Index	≥0.30	≤0.30	≤0.20
Proportion of screened with significant CAD (%)	≤30	30-40	≥40
Patient consent from eligible patients (%)	<30	30-50	>50
Emergency unblinding (%)	> 10	5-10	<5

Table 3 – Criteria for progression following the 12-month internal pilot study.

During the internal pilot detailed screening data will be collected to determine whether there are inclusion or exclusion criteria which are impacting recruitment. Achievement of the green criteria will lead to direct continuation of the trial unchanged. Meeting several amber criteria will lead to discussions between the Trial Management Group, Trial Steering Committee and funder to determine what protocol amendments are needed. Meeting several red criteria will lead to discussions as to whether the trial will continue and, if so, what amendments are needed.

## **6.10 Schedule of assessments for each visit**

### **6.10.1 Baseline visit**

Eligible participants with HFpEF and significant coronary artery disease will attend one-stop outpatient HFpEF clinic and study visit. All investigations will be co-ordinated by the trial team to occur within this visit unless the person wishes otherwise in which case alternative arrangements will be made. Their visit will be supported by the trial research nurse, who will co-ordinate appointments and guide them through the procedures. During this visit the participant will have a clinical review by the unblinded PI, who will optimise their treatment for HFpEF and either manage or refer for optimal management of comorbidities, as per current treatment guidelines.

The participant will undergo the following baseline assessments:

- Measurement of vital signs
  - Heart rate
  - Blood pressure
  - Arterial oxygen saturations (pulse oximetry)
  - Weight
  - Height
- Medical history
  - Past medical history
  - Medication history
  - Social history
- Health status
  - Kansas City Cardiomyopathy Questionnaire
  - New York Heart Association functional class
  - Canadian Cardiac Society angina class
- Blood tests for cardiac biomarkers and pre-PCI testing
  - Full blood count
  - Full lipid profile
  - Renal function

- Troponin
- NT-pro-BNP
- 12-lead ECG
- Three-dimensional transthoracic echocardiogram

### **6.10.2 PCI procedure visit**

The following assessments will be recorded in the eCRF during the PCI procedure visit

- Pre-PCI health status
  - Kansas City Cardiomyopathy Questionnaire
  - Medication history
- Pre-PCI intracoronary physiology (all target lesions)
  - Fractional flow reserve
  - Index of microvascular resistance/myocardial resistance reserve
- Left ventricular end diastolic pressure
  - At rest
  - During handgrip exercise
- Group allocation
- PCI procedure details (in PCI group)
  - As per standard NICOR dataset
- Coronary anatomy
  - BCIS Jeopardy Score
  - SYNTAX Score
- Post-PCI intracoronary physiology (all target lesions)
  - Fractional flow reserve
  - Index of microvascular resistance/myocardial resistance reserve
- Intracoronary imaging and angiography data to be anonymised and retained for core laboratory analysis
- 12-lead ECG
- Post-PCI cardiac biomarkers
  - Troponin

### **6.10.3 Discharge**

- Procedural events and complications
- Blinding questionnaire
- Adverse events/serious adverse events

## **6.11 Follow-up Procedures**

All follow-up procedures will be supervised by the blinded PI and research nurse.

**Three months post-randomisation:** Participants will have the option of either attending in person or via a telephone appointment depending on their preference.

The following assessments will be recorded in the trial eCRF:

- Health status
  - Kansas City Cardiomyopathy Questionnaire
  - New York Heart Association functional class
  - Canadian Cardiovascular Society angina status
- ICHOM standard outcome set for heart failure
  - Mortality
  - Medication (including changes to prescribed clopidogrel/placebo clopidogrel)
  - Medication side effects
  - Financial burden
  - Complications of treatment
  - Number of hospital appointments
  - Number of hospital readmissions
  - Length of stay
- Adverse events/serious adverse events

**Six months post-randomisation (end of trial):** Participants will attend for an in-person appointment where all baseline study assessments will be repeated. Research follow-up will conclude after all six-month assessments have been completed at which point participants will be informed of their treatment assignment. The PI will discuss further treatment, including offering PCI to participants in the placebo procedure group. All participants will be offered ongoing clinical follow-up.

The following assessments will be recorded in the trial eCRF:

- Health status
  - Kansas City Cardiomyopathy Questionnaire
  - New York Heart Association functional class
  - Canadian Cardiovascular Society angina status
- ICHOM standard outcome set for heart failure
  - Mortality
  - Medication (including changes to prescribed clopidogrel/placebo clopidogrel)
  - Medication side effects
  - Financial burden
  - Complications of treatment
  - Number of hospital appointments
  - Number of hospital readmissions
  - Length of stay
- 12-lead ECG
- Biomarkers for heart failure status
  - Troponin
  - NT-pro-BNP
- Transthoracic echocardiogram
- Adverse events/serious adverse event

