#### Outcome measures:

- **Primary efficacy:** The primary efficacy outcome is the difference in KCCQ-OSS between treatment groups at 6-month follow-up. The Kansas City Cardiomyopathy Questionnaire (KCCQ) is the most widely used disease-specific tool for patient reported quality of life outcomes in heart failure, has been specifically validated in HFpEF and is the recommended tool for assessing functional and psychosocial outcomes in the International Consortium for Health Outcomes Measurement (ICHOM) standard outcome set for heart failure published in 2020.
- **Primary mechanistic:** The primary mechanistic outcome is the difference in CFR between treatment groups, after PCI has been performed in the PCI group. CFR is an independent predictor of future adverse cardiovascular events and allows us to determine the relationship between the severity of epicardial and microvascular disease and quality of life.
- **Secondary outcomes:** Key secondary outcomes include all-cause death and hospitalisation for heart failure. Further secondary outcomes include the efficacy of blinding (assessed using standard tools), the ICHOM standard outcome set for heart failure, individual components of the KCCQ (including total symptom score and clinical summary score), New York Heart Association (NYHA) functional class, difference in NT-pro-BNP at six months and difference in left ventricular ejection fraction (LVEF) and diastolic function (mitral E/e') at six months.
- **Secondary mechanistic:** Secondary mechanistic outcomes include change in invasively measured FFR, CFR and microvascular resistance from pre- to post-PCI in all target coronary arteries measured during the PCI procedure.

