## 12 COMPLIANCE AND WITHDRAWAL

### 12.1 Participant compliance

Participants will be encouraged to complete all study procedures and assessments at the appropriate timepoints or at the closest practicable timepoint. Where a participant has not attended a follow-up appointment, site teams will make every effort to contact them using all available telephone numbers and email. If a participant is uncontactable after these initial efforts, research team members will send a letter to the participant requesting them to contact the team. The clinical team and patient's general practitioner will also be contacted to ascertain if there is a reason they have not been able to contact the participant and attempt to facilitate contact.

If participants are unable to be contacted despite persistent efforts from the research team, they will be considered lost to follow-up. Local teams will use patient health records and searches of national registries will be used to confirm vital status. Completeness of follow-up for the primary endpoint will be determined from the trial eCRF and reported. As the trial allocation is to an initial intervention, details of ongoing compliance with treatment are not relevant and will not be recorded.

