### 12.2 Withdrawal / dropout of participants

Participants are free to withdraw from the trial at any time and without having to provide a reason. Their clinical care will not be disadvantaged by their withdrawal from the study.

At the time of withdrawal, participants will be offered three options for withdrawal:

1. Participants may withdraw from active follow-up and further communication but allow the trial team to continue to access their medical records and any relevant hospital data that are recorded as part of routine standard of care; i.e., blood tests, echocardiograms and available measures of health status (e.g. NYHA class and CCS class).
2. Participants can withdraw from the study but permit data and samples obtained up until the point of withdrawal to be retained for use in the study analysis. No further data or samples would be collected after withdrawal.
3. Participants can withdraw completely from the study and withdraw the data and samples collected up until the point of withdrawal. The data and samples already collected would not be used in the final study analysis. (Any limits to this type of withdrawal where, for example analysis of their data or samples has already been integrated into interim results, should be explained in the participant information sheet).

In situations where the participant withdraws but does not specifically indicate a preference, data and samples obtained up until the point of withdrawal will be retained for use in the study analysis. No further data or samples would be collected.

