#### 12.2.1 Recording participant withdrawal in the eCRF

Details of the participant withdrawal will be completed by the CTU team via the Participant Withdrawal form in the eCRF, including reasons for withdrawal where given. Immediately prior to withdrawal, participants will be asked if they consent to completing a final follow-up for completion of the primary outcome data.

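### The 6-month KCCQ, the primary outcome, has no stated remote route for participants who cannot attend, although telephone completion is accepted at 3 months

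*Protocol*

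**What the plan says.** Protocol 5.1 fixes the primary outcome: "The primary efficacy outcome is the difference in KCCQ-OSS between treatment groups at 6-month follow-up".

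Section 6.11 treats the two follow-up contacts differently. At 3 months, with the KCCQ among the assessments, "Participants will have the option of either attending in person or via a telephone appointment depending on their preference". At 6 months, "Participants will attend for an in-person appointment where all baseline study assessments will be repeated". No alternative mode is given for 6 months.

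Section 12.1 asks that assessments be done "at the appropriate timepoints or at the closest practicable timepoint", without a window. Sites pursue non-attenders by telephone, email and letter, and through the clinical team and GP. The stated aim is to restore contact; remote completion of the KCCQ is not mentioned.

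Section 12.2 gives three withdrawal options. Under the mildest, "Participants may withdraw from active follow-up and further communication but allow the trial team to continue to access their medical records"; the examples of health status still available are NYHA and CCS class, not the KCCQ. The other two options end data collection, as does the default when no preference is expressed. Section 12.2.1 adds: "Immediately prior to withdrawal, participants will be asked if they consent to completing a final follow-up for completion of the primary outcome data".

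**The concern.** The echocardiogram, ECG and blood tests at 6 months need attendance. The KCCQ is a questionnaire and does not, as the 3-month contact shows. The remote alternative is missing only at the time point that decides the trial.

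Eligibility covers NYHA class II to IV, and hospitalisation is an expected outcome, so some participants will foreseeably be unable to travel at 6 months. That they would tend to have the lowest scores is an inference, but a reasonable one. If their number differs by arm, the comparison at 6 months is biased. An analysis plan can model such a loss but cannot recover scores that were never collected.

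A second, smaller matter is the KCCQ taken on the day of withdrawal. It is described as serving the primary outcome, at whatever time it falls, and the protocol does not say which time point it belongs to.

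**Working it through.** **1. The plan's own figure.** Inputs from Protocol 16.1: 350 participants, 10% loss, SD 25, correlation 0.6, difference 7, alpha 0.05 (taken as two-sided; the protocol does not say). Allocation is 1:1.

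- Evaluable: 350 × 0.90 = 315, or 157.5 per arm.
- Residual SD after baseline adjustment: 25 × √(1 − 0.6²) = 20.
- Standard error of the difference: 20 × √(2/157.5) = 2.254.
- 7 / 2.254 = 3.11, giving power of 87.4%. The plan states more than 85%.
- The same calculation gives 90.5% at correlation 0.65 (stated above 90%) and 82.0% at SD 27 (stated above 80%).

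The sample size reproduces and is not in question. Power falls below 85% only at about 17% loss and below 80% at about 27%, so lost power at the planned 10% is not the issue either.

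**2. Selective loss.** Let m be the proportion in an arm without a 6-month KCCQ. Let g be the number of points by which their true scores fall below what the model predicts from their observed scores, taken as equal in both arms. Each arm's mean is then overestimated by m × g, and

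bias in the difference = g × (m on PCI − m on placebo).

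The protocol gives no values for g or for loss by arm, so these are assumptions. Every row below averages the planned 10%.

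| Loss PCI | Loss placebo | g = 10 | g = 20 |
|---|---|---|---|
| 10% | 10% | 0 | 0 |
| 8% | 12% | −0.4 | −0.8 |
| 5% | 15% | −1.0 | −2.0 |
| 12% | 8% | +0.4 | +0.8 |

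In the 8% v 12% row, 14 of 175 and 21 of 175 are lost, 35 in all. The shift is 0.4/7 = 6% to 0.8/7 = 11% of the target difference, or 0.4/2.254 = 0.18 to 0.8/2.254 = 0.35 of a standard error. The last row shows that the sign depends on which arm loses more.

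**3. Routes by which a 6-month KCCQ can be obtained.**

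| Situation | Stated route |
|---|---|
| Can attend | In-person visit (6.11) |
| Cannot attend on the day, can later | Later visit, no window (12.1) |
| Cannot attend at all, reachable by telephone | None stated |
| Stops visits, would accept a call | None stated; 12.2 offers records only or no further data |
| Leaves before 6 months | Follow-up at withdrawal, time point unassigned (12.2.1) |

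Rows three and four are the gap.

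**The case against.** Several counter-arguments have weight. The difference in visit mode has a reason: the 6-month contact includes the echocardiogram, ECG, troponin and NT-pro-BNP, and allocation is disclosed once the assessments are done. Section 12.1 lets a temporarily unwell participant be seen later and makes sites work to reach non-attenders. Nothing forbids a telephone KCCQ at 6 months; the text is silent. The 3-month KCCQ enters the mixed model, so people who cannot travel may still contribute a score after randomisation. Someone who declines all contact cannot be asked for a questionnaire, and someone merely unable to attend need not withdraw.

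All of this stands, and it softens the point without closing it. The reason for attendance applies to the tests and not to the questionnaire. A later visit does not help someone who stays housebound. The model deals with loss explained by observed scores, but not with loss driven by the participant's state at 6 months. Visit mode and withdrawal options belong to the protocol and the consent forms, not to an analysis plan.

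A reader might go further and infer from 12.2.1 that a score taken, say, three weeks after randomisation replaces the 6-month score. The protocol does not say so. Section 5.1 fixes the outcome at 6 months, section 16 specifies a model with categorical time points, and the SAP, which is not at hand, may settle how exit scores are assigned. If substitution did happen in a proportion w, with scores carrying a share s of the 6-month effect, a true 7 would be estimated as 7 × (1 − w(1 − s)). With w = 10% this is 6.30 at s = 0 and 6.77 at s = 0.67. The 6.30 is an extreme: the planned 10% also covers people lost to follow-up, who give no exit score.

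**Conclusion.** The point holds as a gap in how the primary outcome is collected. No remote 6-month KCCQ is stated for participants who cannot attend, although the trial accepts one at 3 months, and no withdrawal option preserves it. The likely consequence is selective loss, partly mitigated by section 12.1 and by the 3-month score in the model.

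The size is modest and rests on assumption. It is 0.4 to 0.8 points towards no effect if 12% are lost on placebo and 8% on PCI with a 10 to 20 point shortfall beyond prediction. It is zero if loss and shortfall are equal across arms, and of opposite sign if PCI loses more. The documents do not support saying that the frailest participants will lose their score, only that this is plausible.

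The wording of 12.2.1 is an ambiguity to resolve, not a stated substitution of an early score for the 6-month one. The sample size is unaffected. The change is worth making because it is cheap now and impossible once follow-up has ended.

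**What to change.** - **6.11:** keep the in-person visit as the default at 6 months, but allow the KCCQ to be completed by telephone or post when the participant cannot attend, and record the mode in the eCRF.
- **12.2:** add an option for participants who stop visits but accept contact: one remote KCCQ at 6 months.
- **12.2.1:** record a KCCQ taken at withdrawal under its actual date, state that it is not the 6-month value, and reword the phrase that ties it to the primary outcome.

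The cost is protocol wording, matching text in the consent and withdrawal forms, and one eCRF field. The small downside is a mix of completion modes at 6 months, which the trial already accepts at 3 months and which the recorded mode allows to be examined.

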## 6.12 Trial schedule

	STUDY PERIOD					
					Follow-up	
TIMEPOINT	Screening/ Consent	Baseline Visit	Procedural Visit	Discharge	3 months post- randomisation	6 months post- randomisation
Eligibility screen	X					
Informed consent	X					
Screening CT-FFR (if required)	X					
Randomisation/allocation			X			
INTERVENTIONS:						
Angiogram and Physiology			X			
PCI Procedure			X			
Placebo Procedure			X			
ASSESSMENTS:						
KCCQ		X	X		X	X
Medical history/NYHA/CCS		X			X	X
Full blood count and U&E		X				
Troponin #		X	X			X
NT-pro-BNP		X				X
ECG		X	X			X
Echocardiogram		X				X
Angiography images			X			
Physiology data			X			
Procedural events and complications				X		
Blinding questionnaire				X		
NSAE/SAE				X	X	X

#Post-procedural troponins should be collected at 6 hours, or immediately prior to discharge if before 6 hours

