## 5.2 Outcome definitions

The following serious adverse events will be collected as secondary outcomes and are expected to occur during this study, and will not require additional reporting as SAEs (see section 7 below). Where possible, definitions are aligned with the ARC-2 consensus document.

Outcome	Endpoint definition
Death	
Death from all-causes can be defined as one of the following classifications:
 
 
Cardiovascular death Defined as any death resulting from cardiovascular causes. This may include death caused by: 
 
a. Acute MI
 
b. Sudden cardiac, including unwitnessed death
 
c. Heart Failure
 
d. Stroke
 
e. Cardiovascular procedures
 
f. Cardiovascular haemorrhage
 
g. Other cardiovascular cause
 
 
 
Non-cardiovascular death Defined as any death not thought to be the result of a cardiovascular cause. This may include death caused by: 
 
a. Malignancy
 
b. Pulmonary causes
 
c. Infection (including sepsis)
 
d. Gastrointestinal causes
 
e. Accident or trauma
 
f. Other non-cardiovascular organ failure
 
g. Other non-cardiovascular cause
 
 
 
Undetermined Defined as death not classified under any other category because of the absence of any relevant source documents. For endpoint determination these deaths will be classified as cardiovascular.
 

Myocardial infarction	
Myocardial infarction will be defined according to the ARC-2 definition below.
 
 
Spontaneous myocardial infarction (prior to or ≥48 hours after PCI/CABG)  Detection of a rise and/or fall of cardiac troponin I or T, with at least one value higher than the 99th percentile upper reference limit (URL) AND symptoms consistent with ischaemia OR dynamic electrocardiogram (ECG) changes (including ≥1mm ST elevation or ST depression, new left bundle branch block (LBBB) or >3mm T-wave
 

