	
inversion OR imaging evidence of new loss of viable myocardium or new regional wall motion abnormality in a pattern consistent with an ischaemic aetiology.
 
2. Periprocedural MI (within 48 hours after PCI/CABG) including index procedure and subsequent unplanned revascularisation
 
Absolute rise in cardiac troponin I or T (from baseline) <math>\geq 35</math> times the URL AND new significant Q-waves or equivalent OR flow-limiting angiographic complications OR new "substantial" loss of myocardium on imaging.
 
Flow-limiting angiographic complications are defined as loss of patency of a major vessel, graft or side branch, embolization, disruption of collateral flow, persistent slow flow or no reflow, major dissection, angiographic new occlusion or flow limiting stenosis in a coronary artery bypass graft or native coronary artery occlusion.
 
3. Significant periprocedural myocardial injury (within 48 hours after PCI/CABG) including index procedure and subsequent unplanned revascularisation
 
Absolute rise in cardiac troponin I or T (from baseline) <math>\geq 70</math> times the URL.

Stroke	
Stroke will be defined using NeuroARC definitions as one of the following classifications:
 
Type 1: Overt Central Nervous System (CNS) injury – Acutely symptomatic brain or spinal cord injury
 
 
Type 1a Ischaemic stroke Sudden onset of neurological signs or symptoms fitting with a focal or multifocal vascular territory within the brain, spinal cord or retina that persist for <math>\geq 24</math> hours or until death, with pathology or neuroimaging that demonstrates either CNS infarction in the corresponding territory (with or without haemorrhage) OR absence of other apparent causes (including haemorrhage), even if no evidence of acute ischaemia in the corresponding vascular territory is detected.
 
 
OR
 
Symptoms lasting <math><24</math> hours with pathology or neuroimaging confirmation of CNS infarction in the corresponding vascular territory.
 
 
Subtype 1aH Ischaemic stroke with haemorrhagic conversions Ischaemic stroke includes haemorrhagic conversions. These should be subclassified as Class A or B when conversion ischemic stroke is the
 

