## **6.5 Intervention**

### **6.5.1 Arranging the trial intervention**

The trial intervention will be performed during a day-case hospital admission. Potential dates for the procedure will be discussed with participants in order to find a suitable date for them, including fit notes for employers and funding for relief carers where the participant is a care provider.

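### Periprocedural MI and injury are defined by troponin rise within 48 hours, but one scheduled sample at 6 hours or earlier can miss later threshold crossings, mainly for the troponin-only injury category

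*Protocol*

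**What the plan says.** Protocol 5.2 introduces its list of events with "The following serious adverse events will be collected as secondary outcomes and are expected to occur during this study", and exempts them from separate SAE reporting. Two of the three categories under myocardial infarction are periprocedural:

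- Definition 2: "Periprocedural MI (within 48 hours after PCI/CABG) including index procedure and subsequent unplanned revascularisation". It needs a troponin rise of at least 35 times the upper reference limit (URL) and one of three supporting findings: Q waves or equivalent, a flow-limiting angiographic complication, or substantial new loss of myocardium on imaging.
- Definition 3: "Significant periprocedural myocardial injury (within 48 hours after PCI/CABG) including index procedure and subsequent unplanned revascularisation". It needs a rise of at least 70 times the URL and nothing else.

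Both measure the same quantity: "Absolute rise in cardiac troponin I or T (from baseline").

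The schedule in 6.12 lists troponin at the baseline visit, the procedural visit and six months. Its footnote fixes the post-procedure timing: "Post-procedural troponins should be collected at 6 hours, or immediately prior to discharge if before 6 hours". Section 6.5.1 adds: "The trial intervention will be performed during a day-case hospital admission". The site table in 6.8.1 has one matching item, "Post procedure ECG and Troponin", with no distinction by arm. No later sample, and no trigger for one, is specified.

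**The concern.** The outcome covers 48 hours, but scheduled measurement stops at 6 hours or sooner. A participant whose troponin rise reaches 35 or 70 times the URL only after that sample will not be counted unless someone draws blood for another reason.

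Definition 3 is the most exposed. It has no symptom, ECG or imaging component that would prompt a second sample. No other category recovers the event either, because definition 1 (spontaneous MI) covers only the time before PCI or CABG and from 48 hours onward.

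The loss would probably be uneven between arms. The sampling rule is the same in both, but the categories are tied to PCI or CABG and the placebo procedure deploys no stent (6.5.4.2). Missed crossings would therefore tend to make PCI look safer than it is. A rate presented as 48-hour incidence would also claim more than the measurements support. The sampling time is fixed in the protocol, so an analysis plan cannot later recover a sample that was not drawn.

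**Working it through.** The protocol gives no expected rate of periprocedural MI or injury and no troponin time course, so it has no figure of its own to reproduce here. The check compares the passages and then does threshold arithmetic under stated assumptions.

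**1. The passages side by side**

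| Item | Section | Content |
|---|---|---|
| Window | 5.2 | Within 48 hours of PCI/CABG, index procedure included |
| Definition 2 | 5.2 | Rise ≥35 × URL and a supporting criterion |
| Definition 3 | 5.2 | Rise ≥70 × URL, troponin alone |
| Scheduled sample | 6.12 | One, at 6 hours or before earlier discharge |
| Next scheduled sample | 6.12 | Six months |
| Stay | 6.5.1 | Day case |

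**2. Direction.** Let M be the maximum rise within 48 hours and s the rise at the scheduled sample. Since s ≤ M, the event s ≥ T implies M ≥ T, but not the reverse. The scheduled sample can miss a crossing and cannot create one. This step needs no assumption about kinetics.

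**3. Effective threshold.** If the sample captures a fraction f of the maximum (s = f × M), an event is counted only when M ≥ T / f.

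| f (assumed) | 35 / f | 70 / f |
|---|---|---|
| 1.00 | 35 | 70 |
| 0.75 | 46.7 | 93.3 |
| 0.50 | 70 | 140 |
| 0.25 | 140 | 280 |

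**4. Illustration for the 70-times category.** Assume the peak rise in the PCI arm is lognormal, with median m between 3 and 8 × URL and log-SD σ between 1.3 and 1.5. None of these values comes from the protocol. With Φ the standard normal distribution function, the captured share is P(M ≥ 70/f) / P(M ≥ 70), where P(M ≥ x) = 1 − Φ(ln(x/m)/σ).

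The two extreme corners at f = 0.5:

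- m = 3, σ = 1.3: ln(70/3)/1.3 = 2.42, so P = 0.77%; ln(140/3)/1.3 = 2.96, so P = 0.16%; share = 20%.
- m = 8, σ = 1.5: ln(70/8)/1.5 = 1.45, so P = 7.41%; ln(140/8)/1.5 = 1.91, so P = 2.82%; share = 38%.

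Over the full assumed range:

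| f | Share of 70-times crossings captured |
|---|---|
| 0.25 | 3–12% |
| 0.50 | 20–38% |
| 0.75 | 53–68% |
| 1.00 | 100% |

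The answer runs from almost complete loss to none, depending on a fraction the protocol does not give. The same calculation at 35 times would describe only the troponin part of definition 2, not an MI rate, so it is not used.

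**The case against.** The strongest case against runs as follows. The protocol says nothing about how troponin behaves after PCI, so a loss is possible but not shown. The 48-hour limit separates periprocedural from spontaneous MI; it is not a sampling schedule, and a single draw suits a day case. Definition 2 also needs evidence that is partly collected: the procedural ECG and retained angiography (6.10.2) and the record of procedural complications at discharge (6.10.3). A participant with an overt complication may stay in hospital and have later clinical samples. Nothing forbids these, and 13.1 draws on notes and electronic records. The primary KCCQ-OSS outcome, death and heart failure hospitalisation, and the win ratio are untouched.

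Most of this stands, and it limits the point. A reader might infer that infarctions in the PCI arm will be under-counted and the safety comparison biased by a known amount. The documents do not support that. They give neither a time course nor an event rate, MI does not rest on troponin alone, and the loss could be nil. A reader might also divide 6 by 48 and say that 12.5% of the window is observed; that ratio says little about how many crossings are seen.

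The direction of any error survives the objection, as does the exposure of definition 3. Later clinical samples are possible, but the protocol neither schedules them nor says that their values count toward these definitions.

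**Conclusion.** The point holds as a mismatch between 5.2 and 6.12. Threshold crossings after the scheduled sample are liable to be missed, by an amount the protocol does not allow anyone to fix. The capture shares above are illustrations that rest on an assumed lognormal peak and an assumed fraction f; if the sample falls at peak there is no loss.

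Any loss would fall mainly in the PCI arm, on the inference that stenting is what produces these rises, and mainly in the troponin-only 70-times category. For MI it is less certain. Only secondary safety outcomes are affected. The correction is worth making because it is cheap and because otherwise a 48-hour incidence could be reported that was not measured.

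**What to change.** Reconcile 5.2 with 6.12:

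- Keep the scheduled sample as it stands (6 hours, or before discharge if earlier). Moving it to discharge for everyone would be worse: it could drop the 6-hour value in participants who stay, and it would tie sampling time to complications.
- Record in the eCRF the hours from the end of the procedure to the sample.
- Enter in the eCRF the highest troponin from any research or clinical sample within 48 hours.
- In 5.2, describe definitions 2 and 3 as based on one scheduled troponin at up to 6 hours plus any clinical sample within 48 hours, and do not report them as 48-hour incidence.
- Tabulate sampling time and the number of later clinical samples by arm.

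The cost is two eCRF fields, a change of outcome wording and one table. There is no extra blood draw and no longer stay. The safety claim becomes more modest. The later samples will be clinically driven, so ascertainment may differ between arms; the table by arm lets readers see by how much.
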